2 INTRODUCTION

Interpersonal relationships are paramount to achieve adequate performance and conservation of various social roles that individuals have to cover throughout their life, which in turn becomes a determining factor for their social integration and adaptation in the long-term. For this reason, people need a number of cognitive, behavioral and emotional skills that allow and facilitate cohabitation and social exchange.

Schizophrenia is a disorder characterized by the presence of deficits in social and interpersonal functioning, being these key elements in its definition, in addition to involving a source of stress for the

patients and contributing to relapses and the exacerbation of symptoms¹, also generating enormous personal, socio-family, healthcare and economic costs².

In recent decades hundreds of investigations have focused on the study of these non-social cognitive deficits, such as executive functioning, attention or memory³, but in recent years researchers have also included the study of social cognition⁴. The reason lies in the fact that social cognition was included in the list of key cognitive deficits in schizophrenia, largely due to the appearance of empirical evidence that relates social cognition to social functioning^{5,6} and that assigns it a role of mediating variable between basic social cognition or neurocognition and social functioning^{7,8}.

From an operational point of view, we can classify the skills and functions involved in the regulation of social behavior into two categories:

- Social skills⁹, a construct that includes activities such as:
 - Communicate our needs and thoughts.
 - Listen, understand and respond appropriately to other people.
 - Produce and interpret nonverbal communications.
 - Adapt eye contact, facial expressions and body language to social interaction.
 - Regulate our emotions during them.
- Social cognition¹⁰, a construct that includes activities such as:
 - Perception of emotions, both in faces and in people's voices.
 - Social perception, that is, the interpretation of a series of clues about what happens in a given social context and applying social knowledge to develop the most appropriate behavior for said context.
 - Theory of Mind (ToM), understood as the ability we have to realize that others have ideas and intentions different from ours and that allows us to behave with these people in an appropriate way.
 - Attributive style, understood as the tendency that individuals have to explain the events that happen to them in life and that often leads to considering negative events as caused by the bad intentions of others.

People with schizophrenia tend to isolate themselves, showing little initiative and motivation towards activities, especially social ones, than before the onset of the illness. They suffer from social isolation because they find it difficult to establish contact with other people and carry on a conversation, they have difficulty functioning normally under stressful conditions, in part due to their difficulties in social skills and problem solving.

3 OBJECTIVES AND PURPOSE OF THE STUDY

3.1 MAIN OBJECTIVE

Assessing the efficacy of a cognition and social competence training program (e-Motional Training) in patients with schizophrenia in improving basic emotion recognition, social cognition, emotional intelligence and social competence.

3.2 SECONDARY OBJECTIVES

Improving the cognitive functions of people with severe mental disorder.

Improving employment outcomes.

4 METHODS

4.1 DESIGN

A single-blind randomized clinical trial (Annex I) will be carried out in patients suffering from schizophrenia and who have the legal capacity to consent. Study participants will be randomized to either the experimental group (e-Motional Training) plus Individual Placement and Support (IPS) or the control group (IPS alone).

Sample size calculation:

Taking as a reference the results of the pilot study in schizophrenia carried out by the research team in Galicia ([name] et al), where the average reached in the group before the intervention in the Stories of Theory of Mind by F. Happé in his Spanish version by Pousa (1999) was 8.5 points with a standard deviation of 3.61 points and where, after the intervention, the mean score achieved was 11.67 and the standard deviation was 4.72, for a power of 80% and a confidence level of 95%, the necessary sample in each group would be 30 patients, assuming losses of 5%. An attempt will be made to obtain a total sample of 80 people, taking into account losses during follow-up.

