4.3 MAIN AND SECONDARY VARIABLES

Main study variables: improvement in the recognition of basic emotions, social cognition, emotional intelligence and social competence.

Secondary variables: improvement in symptoms and work results.

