5 WORK PLAN

The purpose of this study is to assess the efficacy of a multicomponent social skills training program in people with schizophrenia.

The expected duration of the study will be one year and will be carried out at the Sinpromi center. Participants will be randomly assigned to receive employment support (IPS control group) or employment support with cognitive rehabilitation (ET + IPS experimental group).

The experimental group (e-Motional Training + Individual Placement and Support) will receive a total of twelve sessions (one hour and a half per week for four months) for training. The training program will consist of the individual practice of tasks related to social skills through the use of an interactive video game, using a computer. During the training, a member of the research team will be present to answer questions. This program has been developed and initially tested by the Psychiatry Service of the Hospital Complex in Ourense.

To assess the level of social cognition, both groups will perform an evaluation before and after rehabilitation to determine whether the intervention has been advantageous or not (blinded investigator).

In addition, once the rehabilitation is finished, the two study groups will be searched for employment and all their variables will be analyzed, such as hours worked, maintenance, salary, etc.

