Statistical analysis plan

Online Training Program on Social Cognition for Patients With Schizophrenia

NCT ID not yet assigned

ULaguna
18-12-2019

Study title: TRAINING IN COGNITION AND SOCIAL COMPETENCE IN PATIENTS WITH SCHIZOPHRENIA

A single-blind randomized clinical trial will be carried out in patients suffering from schizophrenia and who have the legal capacity to consent to the study. Study participants will be randomized to either the experimental group (e-Motional Training) plus Individual Placement and Support (IPS) or the control group (IPS alone).

For data analysis, taking into account that not all patients will have pre and post information, general mixed models will be used with identification of the subject and repeated time measurements (pre and post).

It will be carried out for the analysis of the mean tests as variance (t-student test of independent samples and Levene's test of equality of variances),

The efficacy of a training program in cognition and social competence (e-Motional Training) will be evaluated in patients with schizophrenia when improving the recognition of basic emotions, social cognition, emotional intelligence and social competence.

INFORMATION ON THE USE OF RESOURCES AND FUNDING

(mandatory compliance)

Do you need funding for this study?				YES		NO	X
Do you have required funding for this study?				YES	X	NO	
How many hours of your time during work hours will you dedicate to this study?				25%			
Do you have the material means (equipment, techniques, others...)?				YES	X	NO	
Where will the study take place?							
CONSULTING ROOM	DAY HOSPITAL		UICEC		HOSPITALIZATION	X	OTHERS SINPROMI
Will additional tests be performed outside of routine clinical practice?*				YES		NO	X
*If YES, indicate below:							
Use of biological samples:				YES		NO	X
*If YES, indicate their location below:							
SERVICE / DEPARTMENT: PSYCHIATRY SERVICE. ULL.							
COLLECTION				YES		NO	X
BIOBANK				YES		NO	X
Use of patient clinical data:							
Transfer of encrypted data (pseudonymized) outside the EU to the entities of our group, to service providers or to scientific researchers who collaborate with us				YES		NO	X

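### Protocol section 4.1 sizes a two-arm comparison from one pilot group's before-to-after gain (3.17 points) and states no control-arm change or between-arm difference

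*Protocol*

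**What the plan says.** The sample size paragraph in Protocol section 4.1 takes its figures from a pilot study. It cites "the average reached in the group before the intervention in the Stories of Theory of Mind" (8.5 points, SD 3.61) and then the same group's result once trained: "after the intervention, the mean score achieved was 11.67 and the standard deviation was 4.72, for a power of 80" per cent, at 95% confidence. It concludes that "the necessary sample in each group would be 30 patients, assuming losses of 5" per cent. It adds: "An attempt will be made to obtain a total sample of 80 people, taking into account losses during follow-up". It names no formula, sidedness, working SD or pre-post correlation.

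The design is a randomised comparison of e-Motional Training plus IPS with IPS alone. Protocol section 5 (WORK PLAN) says that "both groups will perform an evaluation before and after rehabilitation to determine whether the intervention has been advantageous or not". The SAP states that "general mixed models will be used with identification of the subject and repeated time measurements (pre and post", and also lists a "t-student test of independent samples and Levene's test of equality of variances". The SAP contains no sample size calculation of its own.

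Protocol section 4.3 gives the main outcomes as constructs: "Main study variables: improvement in the recognition of basic emotions, social cognition, emotional intelligence and social competence". It does not name the Happé stories as primary.

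**The concern.** Both pilot means come from one treated group at two times, so their difference is a within-group change. The trial estimates something else: the change under training plus IPS minus the change under IPS alone. The two are equal only if IPS-alone patients do not change on average. A pre-to-post gain can also contain retest practice, regression to the mean and other change unrelated to training, and the control arm exists to remove these.

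This paragraph is the only justification of the trial's size. As written, a reader cannot tell which between-arm difference the trial was sized to detect, or how much improvement under IPS alone it could tolerate.

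**Working it through.** **Inputs from Protocol 4.1.** Means 8.5 and 11.67; SDs 3.61 and 4.72; power 80%; confidence 95%; 30 per group with 5% losses; target total 80.

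**Assumed, because the documents are silent.** Two-sided 5% unless noted; 1:1 allocation; 5% loss applied to the 80, so 40 × 0.95 = 38 evaluable per arm; the control gains and pre-post correlations shown below.

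**Step 1: reproduce the 30.**
- Gain: 11.67 − 8.5 = 3.17.
- Averaged SD: √[(3.61² + 4.72²)/2] = √17.655 = 4.20.
- Two-sample formula: n = 2(1.960 + 0.842)² × SD² / difference² = 2 × 7.849 × 17.655 / 10.049 = 27.6, so 28 per arm.
- Losses: 28/0.95 = 29.5, so 30. This matches the stated figure.

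**Step 2: other routes.**

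| Route | n | After 5% losses |
|---|---|---|
| Two groups, two-sided, SD 4.20 | 27.6 → 28 | 30 |
| Two groups, one-sided, SD 4.72 | 27.4 → 28 | 30 |
| Two-arm change scores, correlation 0.52 (change SD 4.19) | 27.5 → 28 | 30 |
| One group, paired, correlation 0 (change SD 5.94) | 27.6 → 28 | 30 |
| Two groups, two-sided, SD 4.72 | 34.8 → 35 | 37 |
| One group, paired, correlation 0.3 / 0.5 / 0.7 | 20 / 15 / 9 | 22 / 16 / 10 |

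All four routes that reach 30 enter the full 3.17. The first three compare two arms with control change set to zero. In the two post-score versions, the pilot mean before training stands in for the control arm's follow-up mean. The fourth tests one group's own change and says nothing about a control arm.

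**Step 3: power at the planned 80.** Two-sided t-test, 38 evaluable per arm, difference = 3.17 minus an assumed control gain. Adjusted SD = SD × √(1 − 0.5²), at an assumed correlation of 0.5.

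| Analysis SD | Gain 0 | 0.5 | 1.0 | 1.5 | Difference at 80% power | Control gain tolerated |
|---|---|---|---|---|---|---|
| 4.20 unadjusted | 90% | 78% | 60% | 40% | 2.74 | 0.43 |
| 4.72 unadjusted | 82% | 68% | 51% | 33% | 3.07 | 0.10 |
| 3.64 (4.20 adjusted) | 96% | 88% | 73% | 51% | 2.37 | 0.80 |
| 4.09 (4.72 adjusted) | 92% | 80% | 63% | 42% | 2.66 | 0.51 |

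The tolerated gain is 3.17 minus the difference at 80% power. With 10% loss instead (36 per arm) and no control gain, unadjusted power is 88% at SD 4.20 or 80% at SD 4.72.

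**Step 4: the stated 30 per group (28 evaluable).** With no control gain and SD 4.20, unadjusted power is 81% by the normal formula and 79% by the t-test, so nothing is left to absorb a control gain. With baseline adjustment at an assumed correlation of 0.5, the t-test keeps 80% power up to a control gain of about 0.40 points (SD 4.20) or 0.05 points (SD 4.72).

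**The case against.** The other side has four good arguments.

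- **The formula is inferred.** The protocol names none, and the paired route at correlation 0 also gives 30 without assuming anything about controls. This stands as a limit on what can be said about how 30 was obtained. It does not rescue the paragraph: a paired calculation for one group does not size a two-arm contrast, and every matching route still uses 3.17.
- **The SAP's mixed model uses baseline data.** A reader might infer that 80% power is lost under any analysis once controls improve at all. The documents do not support that. Baseline adjustment could absorb some control gain even at 28 per arm: about 0.40 or 0.05 points at correlation 0.5, and 0.88 or 0.60 at 0.7 (SD 4.20 or 4.72). The strict condition applies to the unadjusted comparison. Since no correlation is given, the protocol cannot claim this margin either.
- **Zero control change may be reasonable.** IPS is employment support, section 5 places the job search after the rehabilitation, and nothing shows that IPS alone raises Happé scores. A reader might infer that controls will improve; that is not supported, and the gains tabulated are a sensitivity range. But if no change is assumed, the plan should say so and give a reason.
- **The target is 80, not 60.** A reader might infer that the trial is underpowered. That is not shown: with no control gain, 80 patients give more than 80% power under the assumptions above. The extra patients are, however, attributed to follow-up losses rather than to control improvement, and the unadjusted margin is only 0.10 to 0.43 points.

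**Conclusion.** The point holds and should be fixed. Section 4.1 attaches its 80% power to a within-group gain, while the trial estimates a between-arm difference. For an unadjusted comparison at 30 per group, with the inputs that yield 30, the claim requires no average improvement under IPS alone. Neither document states or supports that requirement.

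The defect is a mis-specified power target. Any actual shortfall is unknown, because no control change is given, and the results depend on the SD, correlation and loss rate chosen. Confidence is high that the control-arm figure is absent and that 3.17 drives the stated 30. It is lower on which formula was used. The conclusion covers the Happé stories only and says nothing about power for the other main outcomes.

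**What to change.** In Protocol section 4.1, replace the 80% claim with a between-arm statement, for example:

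> *With 80 randomised 1:1 and an assumed 5% loss (38 evaluable per arm), a two-sided 5% unadjusted t-test has 80% power for a between-arm difference of 2.74 points on the Happé stories at post-training (SD 4.20).*

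If SD 4.72 is preferred, the difference is 3.07 points; keep one SD throughout.

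In a separate sentence, justify that difference as the pilot gain of 3.17 minus the expected IPS-alone change. It is reached if that change is at most 0.43 points (0.10 at SD 4.72). Use pilot control data if they exist. The expected control change belongs in this justification, because power for a given between-arm difference does not depend on it.

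State the loss rate applied to the 80, since the 5% in section 4.1 is attached to the 30. If a baseline-adjusted SD is used, state the correlation.

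The cost is rewording one paragraph, with no extra enrolment. The downside is that the justification may look less favourable once the control-arm assumption is visible.

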4.2.1 INCLUSION CRITERIA

The inclusion criteria will be the following:

- ✓ People with severe mental disorder between 18 and 50 years old.
- ✓ Have the diagnosis schizophrenia according to DSM-V criteria.
- ✓ The patient has the capacity to consent.
- ✓ Having given their free consent to participate in the study, once informed about its objectives.
- ✓ Be a patient under the Psychiatry Service of the USMC at the time of the study.
- ✓ Be motivated to get ordinary employment.

4.2.2 EXCLUSION CRITERIA

The exclusion criteria will be the following:

- ✗ Not having given their free consent to participate in the study.
- ✗ Present a severe comorbid mental disorder or present a history of severe brain damage or neurological disorder that may function as a confounding factor, or intellectual disability (examples: associated organic mental disorder or diagnosis of borderline or lower IQ).
- ✗ Inability to work.
- ✗ Current participation in a skills program designed to improve social adjustment.
- ✗ Current abuse of toxic substances (except nicotine).

All patients who meet all the inclusion criteria and none of the exclusion criteria will be included.

4.2.3 CRITERIA FOR THE WITHDRAWAL OF SUBJECTS FROM THE STUDY

- Explicit request from the subject to stop participating in the study.
- Change of place of residence, outside the autonomous community in which the study will be carried out.
- Death of the subject who will participate in the study.

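### Section 4.2.3 withdraws any patient who leaves the region, with no further outcome collection provided for, so the secondary employment comparison may lose data for reasons tied to its own outcome

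*Protocol*

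**What the plan says.** Protocol Section 4.2.3 is headed "CRITERIA FOR THE WITHDRAWAL OF SUBJECTS FROM THE STUDY". It gives three criteria: the subject's own request, death, and "Change of place of residence, outside the autonomous community in which the study will be carried out". The heading refers to the study, not only to the training, and the relocation criterion applies whatever the reason for the move.

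Employment is part of what the trial sets out to study:

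- Section 3.2 (secondary objectives) includes "Improving employment outcomes".
- Section 4.3 states: "Secondary variables: improvement in symptoms and work results".
- Section 4.2.1 requires every participant to "Be motivated to get ordinary employment".
- Section 5 (Work plan) gives employment support to both arms: "Participants will be randomly assigned to receive employment support (IPS control group) or employment support with cognitive rehabilitation (ET + IPS experimental group)".
- Section 5 also says that, after rehabilitation, "the two study groups will be searched for employment and all their variables will be analyzed, such as hours worked, maintenance, salary, etc".

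The SAP expects some patients to lack pre or post data and answers this with a mixed model on repeated pre and post measurements. It also names an independent-samples t-test with Levene's test, without saying which variables they apply to. Neither document states an analysis or a missing-data rule for the work outcomes, an intention-to-treat rule, or any remote follow-up after withdrawal.

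**The concern.** Withdrawal for relocation happens after randomisation and can be a consequence of the outcome. A participant who takes a job in another region has succeeded on the employment measure, and that success triggers the withdrawal rule. Missingness of this kind depends on the value that would have been observed, so it cannot be assumed ignorable.

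The mixed model does not clearly help. It works on scores measured before and after training. Hours worked, job maintenance and salary are described only as measures taken after rehabilitation, so there is no pre/post pair for such a model to use. A t-test on these variables would use only patients who have a value.

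At stake are the employment results within each arm, the comparison between arms, and the completeness of a small trial. Of the three criteria, a subject's request and a death are outside the investigator's control. Relocation is different: losing outcome data because of it is a choice made in the protocol, and work outcomes can be obtained without a site visit.

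**Working it through.** **The plan's own figure.** The only sample-size figure concerns the Happé stories (Section 4.1), not employment. With a difference of 11.67 − 8.5 = 3.17, a pooled SD of √((3.61² + 4.72²)/2) = 4.20, two-sided 5% significance (sidedness assumed) and 80% power, the normal-approximation formula gives 28 per group. Allowing for 5% losses, 28/0.95 = 29.5, which rounds up to the stated 30. There is no arithmetic fault there, and this point does not depend on it.

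**Inputs for the illustration.**

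- 40 per arm: the target total of 80 in Section 4.1, split equally. The allocation ratio is not stated, so 1:1 is assumed.
- True employment of 50% (20/40) with e-Motional Training plus IPS and 30% (12/40) with IPS alone. Both are assumed, because the documents give no employment rate. The true difference is 20 points.
- Numbers of movers: assumed, because the documents give no relocation rate.
- Handling of movers: dropped from numerator and denominator unless stated otherwise. This is also assumed, because the documents do not say.

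**Formulas.** With n patients and e employed in an arm, the observed rate is (e − m)/(n − m) if m employed movers are dropped, and e/(n − m) if m unemployed movers are dropped. If employed movers are instead counted as not employed, it is (e − m)/n.

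| Who moves | Experimental | Control | Difference (points) |
|---|---|---|---|
| Nobody | 20/40 = 50.0% | 12/40 = 30.0% | 20.0 |
| Two employed, experimental arm only | 18/38 = 47.4% | 12/40 = 30.0% | 17.4 |
| Two employed in each arm | 18/38 = 47.4% | 10/38 = 26.3% | 21.1 |
| Two unemployed, experimental arm only | 20/38 = 52.6% | 12/40 = 30.0% | 22.6 |
| Two employed, experimental arm only, counted as not employed | 18/40 = 45.0% | 12/40 = 30.0% | 15.0 |

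**Equal proportions moving.** Suppose 10% of the employed in each arm move and are dropped. The observed rate is p(1 − 0.1)/(1 − 0.1p): 0.45/0.95 = 47.4% and 0.27/0.97 = 27.8%, a difference of 19.5 points. With no true effect (50% in both arms) and equal relocation, the difference stays at zero.

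**What this shows.** Dropping employed movers lowers the observed rate in any arm where it happens. The difference between arms can fall, rise or stay nearly unchanged, depending on which patients move and from which arm.

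**Scale.** At 50% versus 30% with 40 per arm, the 95% half-width on the difference is 1.96 × √(0.5 × 0.5/40 + 0.3 × 0.7/40) = 0.21, or about 21 points. The shifts in the table are small beside that.

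**The case against.** The best case for leaving the rule alone has four parts.

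1. **Employment is secondary.** The main variables are emotion recognition, social cognition, emotional intelligence and social competence. The work search is placed after rehabilitation, so moves prompted by a job would mostly follow the post-training tests. This stands. It confines the point to the secondary comparison.

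2. **The text does not say that movers are deleted.** A reader might infer that a relocated patient leaves the data set. Section 4.2.3 says only that the patient is withdrawn. A job and salary obtained before the move may already be on record, so that what is lost is later hours and job maintenance. This also stands, and it makes complete removal of movers an assumption of the illustration.

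3. **The direction is not established.** A reader might infer that the rule pulls the comparison towards no effect, because a helpful intervention would send more people away to jobs. That requires movers to be mostly employed and mostly from the experimental arm. The rule covers every move, and nothing in the documents shows who would move.

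4. **The numbers may be small.** Section 5 says "The expected duration of the study will be one year" and places it at one local centre, and only moves out of the whole autonomous community count. This is plausible, but the documents give no rate that would settle it.

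In addition, the consent pages are not in the reviewed copy and the Annex I flowchart is incomplete, so a contact clause or a scheme for handling losses may already exist. None of this supplies what the available text lacks: a provision to keep collecting work outcomes after a move.

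**Conclusion.** The point holds as a limited one. Section 4.2.3 withdraws relocated patients from the study whatever their reason for moving, and the available text has no provision for further outcome collection. Because a move can result from getting a job, this may cause avoidable, outcome-dependent missing data in the secondary employment comparison. The main pre/post measures are largely unaffected.

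The size cannot be determined from the documents. In the illustration, two movers in an arm shift a 20-point difference by about 1 to 3 points if dropped, in either direction, and by 5 points downwards if employed movers from the experimental arm are counted as not employed. These figures rest on assumed employment rates, mover numbers and handling. They do not support a claim of bias towards no effect, or a claim that the trial's main conclusions are at risk.

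The change is still worth making. Complete follow-up removes the problem whichever direction it would take, whereas employment data never collected after a withdrawal cannot be recovered in the analysis.

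**What to change.** In Section 4.2.3, either remove relocation as a reason to end study follow-up, or keep the line and state that outcome follow-up continues after a move. Then add the following:

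- Relocated patients stay in their randomised arm in the analysis.
- Employment status, hours, job maintenance and salary are collected by telephone or work record over the same period as for other patients. Section 5 gives no length for that period, so it needs to be stated.
- The date of the move and the reason for it are recorded.
- Only test-battery scores that cannot be obtained are treated as missing in the SAP's mixed model.

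The cost is a line or two in the protocol, a few telephone calls and, if not already present, a contact clause in the consent form. Test scores may be less complete for relocated patients. The change concerns outcome data only and says nothing about the care a relocated patient receives.
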